| Study design: | 
This is a retrospective, multi-center, cohort study to collect the data on COPD patients who were administered with LABA/LAMA (FDC or free combo) or LAMA treatment for 3 months at least prior to 30 June 2018. For LABA/LAMA therapy, new initiation or switching from other therapy (i.e., single/dual/triple) are both acceptable; for LAMA
 | | |

Proprietary confidential information © 2019 Boehringer Ingelheim International GmbH or one or more of its affiliated companies

| | |
|--------------------|---|
| | 
treatment, only new initiation will be acceptable. The data abstracted from eligible patients will be recorded only when they are available in the medical chart and will be categorized into the cohort A (patients treated with Tio + Olo), B (patients treated with other LABA/LAMA therapy), and C (LAMA therapy).
 
The follow-up period for each patient will be from the index date* until the date of death or 1 year after the index date, whichever occurs first. Patients will be censored at the time from one LAMA/LABA or LAMA switched to another LAMA/LABA or ICS.
 
*Index date: It is defined as the date of COPD patients in the cohort A and B starting using LABA/LAMA therapy regardless of new initiation or switching from other single/dual/triple treatment, or the date of the patients in the cohort C starting using LAMA treatment.
 |
| Population: | 
This study plans to review the medical chart from approximately 1,800 COPD patients receiving LABA/LAMA or LAMA treatment for 3 months at least prior to June 30 2018 in Taiwan.
 
Inclusion criteria
 
Patients who fulfil ALL the following criteria are included.
 
1. Patients who diagnosed with COPD who were prescribed with LABA/LAMA (FDC or free combo) as a new initiation or switching from other therapy (i.e., single/dual/triple), or newly receiving LAMA treatment for 3 months at least prior to 30 June 20182. Male or female patients ≥ 40 years of age 
Exclusion criteria
 
Patients who meet the following criterion are not included.
 
1. Patients with documented diagnosis of bronchial asthma, asthma-COPD overlap syndrome (ACOS), bronchiectasis, cystic fibrosis, or lung cancer |

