| Variables: | 
Variables
 
• Patient demographics (date of birth, gender, race, body mass index [BMI], family history, occupation, etc.)• Diagnosis of COPD (date of diagnosis, disease severity, etc.)• Smoking status• Spirometry data (e.g., FEV₁, FVC)• COPD assessments (e.g., CAT, mMRC)• Acute exacerbations from 1 year before the index date until 1 year after the index date or the date of death (onset/stop date, etc.)• Hospitalizations due to COPD exacerbation (e.g., admission/discharge date, treatments)• Laboratory data (e.g., eosinophil counts) |

Proprietary confidential information © 2019 Boehringer Ingelheim International GmbH or one or more of its affiliated companies

| | |
|-----------------------|--|
| | 
• Pharmacological/non-pharmacological treatments from 6 months before the index date to 1 year after the index date or the date of death, especially for the following:
- Treatment related to COPD (start/stop dates, dosage, frequency, etc.)- Rescue treatments for COPD (antibiotics, oral corticosteroid, ventilator support, etc.)- Oxygen therapies- Surgeries for COPD therapy or improvement of lung function• Time/reasons for treatment switching (e.g., single/dual/triple therapy to LABA/LAMA prior to the index date, Tio + Olo to other therapies, single/dual escalating to dual/triple therapy)• Comorbidities (cardiovascular, cerebrovascular, respiratory, hepatic, renal, gastrointestinal, metabolic, infectious comorbidities, etc.) |
| | 
Primary outcomes
 
• Time to the first moderate or severe COPD exacerbation |
| | 
Secondary outcomes
 
• Annualized rate of mild/moderate/severe exacerbation• Time/reason (e.g., severe airflow limitation, diagnosis of asthma, worsening exacerbation) from LABA/LAMA escalating to LABA/LAMA/ICS or from LAMA to dual therapy• Percentage of patients receiving LABA/LAMA switched to triple therapy or LAMA switched to dual therapy• Change in pulmonary function after LABA/LAMA or LAMA initiation• Use of rescue medications |
| Data sources: | Source data are collected from medical charts in 12 medical hospitals in Taiwan. The case report form (CRF) will be designed for the data collection. |
| Study size: | Approximately 1,800 eligible COPD patients are planned to be enrolled from 12 medical hospitals in Taiwan. |

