9. RESEARCH METHODS

9.1 STUDY DESIGN

It is a retrospective, multi-center, cohort study to collect the data on COPD patients who were administered with LABA/LAMA (FDC or free combo) or LAMA therapy for 3 months at least prior to 30 June 2018. The patients using LABA/LAMA therapy will be enrolled regardless of new initiation or switched from other single/dual/triple treatment, whereas those using LAMA treatment will only be acceptable when LAMA is newly initiated. This study aims to estimate the occurrence of COPD exacerbation in the COPD population under the real-world practice in Taiwan. Additionally, the study also assesses outcomes of clinical characteristics and prescription patterns for patients using LABA/LAMA or LAMA. After Institutional Review Board's (IRB) permission, it will be carried out in around 12 medical centers in Taiwan and plans to collect the clinical data abstracted from the medical charts of approximately 1,800 eligible patients. The eligible patients will be separated into three cohorts based on the prescription for COPD on the index date. Cohort A includes the patients treated with Tio + Olo, cohort B is the patients treated with other LABA/LAMA therapy, and cohort C is the patients receiving LAMA treatment. No investigational or interventional treatment will be provided in the retrospective study.

The retrospective study will review medical charts of COPD patients with LABA/LAMA or LAMA therapy until death or 1 year after the index date, whichever occurs first. The data collection will be conducted after eligibility assessment. Medical records will be reviewed and relevant information will be abstracted for various details such as patient demographics, diagnosis of COPD, smoking status, records of exacerbations and hospitalization, examinations of lung function and laboratory, treatments related to COPD or comorbidities, reasons for treatment switching, and comorbidities.

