9.2.2 Study population

The data will be retrospectively abstracted from the medical chart after eligibility assessment. Eligible patients will be categorized into the cohort A (patients treated with Tio + Olo), B (patients treated with other LABA/LAMA therapy), and C (patients treated with LAMA therapy).

Inclusion criteria

Patients who fulfil **ALL** the following criteria are included.

1. Patients who diagnosed with COPD who were prescribed with LABA/LAMA (FDC or free combo) as a new initiation or switching from other therapy (i.e., single/dual/triple), or newly receiving LAMA treatment for 3 months at least prior to 30 June 2018
2. Male or female patients ≥ 40 years of age

Exclusion criteria

Patients who meet the following criterion are not included.

1. Patients with documented diagnosis of bronchial asthma, asthma-COPD overlap syndrome (ACOS), bronchiectasis, cystic fibrosis, or lung cancer

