| 11. | If a patient receiving SABA, SAMA, LABA/ICS or a triple therapy before LABA/LAMA treatment on the index date, the relevant information on the medications, doses, frequency, the route of administration, the reasons for switching medications should be recorded. | | | | |
| 12. | Prescription date, doses, and frequency will be recorded. | | | | |
| 13. | Therapies for the emergency/hospitalization regarding COPD (ICD-9: 491.21; ICD-10: J44.1) will be collected, including but not limited to short-acting bronchodilators, antibiotics, oral corticosteroid (e.g., prednisone or prednisolone), ventilator support, or oxygen therapy. Prescription date, doses, frequency, and the route of administration will be recorded. | | | | |
| 14. | NIPPV or IPPV for those not for rescue use | | | | |
| 15. | Including but not limited to surgeries for COPD or improvement of lung function. | | | | |

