9.3.2.2 Secondary outcomes

- Annualized rate of mild/moderate/severe exacerbation
- Time/reason (e.g., severe airflow limitation, diagnosis of asthma, worsening exacerbation) from LABA/LAMA escalating to LABA/LAMA/ICS or from LAMA to dual therapy

Proprietary confidential information © 2019 Boehringer Ingelheim International GmbH or one or more of its affiliated companies

- Percentage of patients receiving LABA/LAMA switched to triple therapy or LAMA switched to dual therapy
- Change in pulmonary function after LABA/LAMA or LAMA initiation
- Use of rescue medications

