9.7.1 Main analysis

The propensity score matching approach* will be used to balance the baseline characteristics between the study cohorts. These data will be compared descriptively between patients receiving different regimens (Tio + Olo vs. other LABA/LAMA vs. LAMA). If the propensity score matching is done, the difference before and after matching will be considered both.

For the primary outcome

Time to the first moderate or severe COPD exacerbation will be compared between different cohorts using Kaplan-Meier curves with the incidence and time to events, and statistical significance will be assessed using log-rank tests.

Time to first acute exacerbation starts from the index date to the date of the first acute exacerbation recorded on the CRF. Patients with exacerbation free at the time of escalating to ICS or no documented with exacerbations will be censored.

For secondary outcomes

- Time to escalating to dual/triple therapy will also be analysed using Kaplan-Meier curves and log-rank tests.
- The annualized rate of exacerbation with various severity will be calculated for each study group (episodes/patient-year), and the differences between the three cohorts will be compared by rate ratio.
- Results of lung function (i.e., spirometry data) and COPD assessments (i.e., CAT and mMRC) will be evaluated by the change from baseline. Pair *t*-test or other applicable statistical methods will be used for assessing the intra-group difference under a significance level of 0.05.
- Chi-square test or Fisher's exact test will be applied for categorical variables such as reasons for switching/escalating therapies, frequency, and percentage, etc.

*NOTE: Variables may include but not limited to age, gender, disease duration before index date, smoking status, body mass index, COPD assessment score (e.g., CAT and mMRC), spirometry data (e.g., FEV₁), oxygen therapy, comorbidities, disease severity, previous exacerbation, previous treatments, or eosinophil counts, where appropriate.

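### The escalation outcomes in cohorts A and B do not separate a first step up to triple therapy from a return to an earlier ICS-containing regimen, so entry route can confound the A-versus-B comparison

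*Combined protocol and SAP*

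**What the plan says.** **Entry.** The abstract (Study design) states: "For LABA/LAMA therapy, new initiation or switching from other therapy (i.e., single/dual/triple) are both acceptable". Sections 9.1 and 9.2.2 repeat this rule, and the index date is the start of LABA/LAMA whichever route the patient took. Cohort C is narrower: "those using LAMA treatment will only be acceptable when LAMA is newly initiated". The only exclusion in 9.2.2 is diagnostic: "Patients with documented diagnosis of bronchial asthma, asthma-COPD overlap syndrome (ACOS), bronchiectasis, cystic fibrosis, or lung cancer". Prior triple therapy or prior ICS use therefore keeps nobody out of A or B.

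**Outcomes.** The abstract and 9.3.2.2 list two relevant secondary outcomes. One is "Percentage of patients receiving LABA/LAMA switched to triple therapy or LAMA switched to dual therapy". The other is the time and reason "from LABA/LAMA escalating to LABA/LAMA/ICS or from LAMA to dual therapy". Neither refers to the regimen before the index date.

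**Analysis.** Section 9.7.1 says: "Time to escalating to dual/triple therapy will also be analysed using Kaplan-Meier curves and log-rank tests". Categorical results, including reasons for switching and percentages, get chi-square or Fisher's exact tests. No restriction or stratification by prior regimen is stated. Previous treatments appear only among the variables that may enter the propensity score, and results before matching are to be considered as well as those after it.

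**Data.** Table 1, note 11, requires details and reasons for switching to be recorded "If a patient receiving SABA, SAMA, LABA/ICS or a triple therapy before LABA/LAMA treatment on the index date". Section 9.3.3.7 sets the look-back for COPD medication at 6 months before the index date.

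**The concern.** A patient who moved from triple therapy to LABA/LAMA at the index date and later went back is counted in the same way as a patient who needed ICS added for the first time in the recorded history. A patient who came from LABA/ICS and then moves to LABA/LAMA/ICS is also resuming ICS. Both enter the escalation curve alongside first step-ups.

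Two things are at stake. The first is interpretation: a curve labelled as escalation is partly a curve of returns, in a proportion that nobody will see. The second is comparison: if one of the two LABA/LAMA cohorts contains more step-down patients, and those patients are more (or less) likely to move to triple therapy, the log-rank and chi-square tests will pick up entry route as well as any difference between drugs.

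**Working it through.** The documents state no expected escalation percentage, no share of patients coming from triple therapy and no power for these outcomes. There is no plan figure to reproduce, and the main check is textual.

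**1. Textual check.** The entry rule admits a switch from triple therapy or LABA/ICS. The outcome rule counts any move from LABA/LAMA to triple. The analysis rule pools these moves within a cohort. Nothing visible connects the recorded prior regimen to the outcome definition.

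**2. When does this distort A versus B?** Let s be the share of a cohort that stepped down from triple therapy, p0 the one-year risk of moving to triple in the other patients, and p1 the risk in step-down patients. Then

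cohort escalation = (1 − s) × p0 + s × p1

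share of escalations from step-down patients = s × p1 / cohort escalation

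With p0 and p1 the same in both cohorts (no drug difference), A minus B = (sA − sB) × (p1 − p0). This is zero if the shares are equal or if the risks are equal. Both must differ for any distortion, and its direction depends on which cohort has the larger share.

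**3. Illustration.** The shares and risks below are assumptions. Only the cohort sizes, about 300 and 800, come from section 9.5. The last column is the probability that a two-sided 0.05 two-proportion test (pooled standard error under the null) rejects, without matching.

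| p0 | p1 | sA | sB | Escalation A | Escalation B | From step-downs, A / B | P(significant) |
|---|---|---|---|---|---|---|---|
| 10% | 10% | 10% | 20% | 10.0% | 10.0% | 10% / 20% | 5% |
| 10% | 30% | 20% | 20% | 14.0% | 14.0% | 43% / 43% | 5% |
| 10% | 20% | 10% | 20% | 11.0% | 12.0% | 18% / 33% | 7% |
| 10% | 30% | 10% | 20% | 12.0% | 14.0% | 25% / 43% | 13% |
| 10% | 30% | 5% | 25% | 11.0% | 15.0% | 14% / 50% | 39% |
| 5% | 30% | 10% | 30% | 7.5% | 12.5% | 40% / 72% | 67% |
| 5% | 30% | 5% | 25% | 6.3% | 11.3% | 24% / 67% | 72% |

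Worked line (fifth row): A = 0.95 × 0.10 + 0.05 × 0.30 = 0.110; B = 0.75 × 0.10 + 0.25 × 0.30 = 0.150; step-down share of events = 0.015/0.110 = 14% in A and 0.075/0.150 = 50% in B.

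**4. What the table shows.** The second row has no A-versus-B distortion, yet the level in each cohort is 14% rather than the 10% that applies to patients who had not stepped down. The mixing of events therefore matters for interpretation even when the comparison is clean. In every row, A equals B within each stratum (for example 10% and 10%, 30% and 30% in the fifth row), so splitting by prior regimen removes the spurious difference.

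**The case against.** **The percentage is right for its stated purpose.** The secondary objectives are clinical characteristics and prescription patterns, and the outcome counts patients switched to triple therapy. A patient who goes back to triple has switched to it. This stands. A reader might infer that the percentage is meant to show how often LABA/LAMA proves insufficient, and is therefore wrong; no section says so. Only the time/reason outcome and the Kaplan-Meier analysis use the word escalating.

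**Matching could remove the A-versus-B bias.** This is correct if prior regimen is in the score and the shares are balanced: equal shares give 5% rejection above. But prior treatment is optional, and unmatched results are also considered. Matching does not change what the event means either. Nor can it align cohort C, which is limited to new LAMA starts and whose event is a move to dual therapy.

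**The data already distinguish these patients.** Prior therapy and reasons for switching are collected, and the reason for escalation is itself an outcome. That makes the repair easy, but the visible percentage, curve and test do not use the information.

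**The size is speculative.** This stands in full. In addition, if the minimum of 3 months of therapy means 3 months on the index regimen, early returns to triple never enter, which makes high return risks harder to assume. Later returns still count.

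**Something may be redacted.** The contents list has a blacked-out entry between 9.7.1 and 9.7.3, so an analysis by prior therapy cannot be ruled out. The visible outcome definitions remain unconditional.

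**Conclusion.** The point holds as a matter of definition and of potential confounding. The escalation outcomes for A and B pool first step-ups with returns to an earlier ICS-containing regimen. The A-versus-B tests are open to confounding by entry route under two conditions together: unequal step-down shares, and a different risk of triple therapy in those patients.

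It would go too far to say that the comparison is biased, or by how much. The documents give none of the rates needed, and the illustrations run from no distortion (5%) to a 72% chance of a spurious significant result, the latter only with strongly unequal shares and risks and no effective matching. The documents also do not support calling the overall switched-to-triple percentage invalid.

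The matter is confined to secondary outcomes; this labelling does not touch the definition of time to first moderate or severe exacerbation. It is still worth correcting, because the repair uses data already on the CRF.

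**What to change.** In the abstract, 9.3.2.2 and 9.7.1:

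- Keep the overall percentage switched to triple therapy as a description of prescribing.
- Report the escalation percentage and Kaplan-Meier curves for A and B separately by regimen in the 6 months before the index date: triple therapy, LABA/ICS, or no ICS.
- In patients with prior triple therapy, label a later move to triple as a return to triple, not an escalation.
- Stratify the A-versus-B log-rank test by this factor.
- Make prior regimen a required propensity-score variable.

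Simply dropping patients stepped down from triple therapy would be a weaker repair. It would discard data and still count prior LABA/ICS users as first escalations.

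The cost is plan wording and one derived variable, with no new data collection. The strata will be smaller: with an assumed 5% step-down share, cohort A would have 0.05 × 300 = 15 such patients, too few for more than description. Triple or ICS use more than 6 months before the index date is not seen, so the no-ICS group cannot be described as never exposed.

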| Data analysis: | A Data Validation Plan (DVP) will be prepared to describe the processes for data validation. The data abstracted from the medical chart will be described with number, mean, standard deviation (SD), range, and 95% confidence intervals (95% CI) for continuous variables, and frequencies and percentages for categorical variables. |

Proprietary confidential information © 2019 Boehringer Ingelheim International GmbH or one or more of its affiliated companies

| | |
|--------------------|--|
| | 
The propensity score matching approach* will be used to balance the baseline characteristics between the study cohorts (Tio + Olo vs. other LABA/LAMA vs. LAMA therapy).
 
These data will be compared descriptively between patients receiving different regimens (Tio + Olo vs. other LABA/LAMA vs. LAMA therapy). If the propensity score matching is done, the difference before and after matching will be considered both.
 
The annualized rate of exacerbation with various severities will be calculated for each study group (episodes/patient-year), and the differences between the three cohorts will be compared by rate ratio.
 
Time to the first moderate or severe COPD exacerbation or escalating to dual or triple therapy will be compared between different cohorts using Kaplan-Meier curves with the incidence and time to events, and statistical significance will be assessed using log-rank tests.
 
Chi-square test or Fisher's exact test will be applied for categorical variables such as reasons for switching/escalating therapies, frequency, and percentage, etc.
 
*NOTE: Variables may include but not limited to age, gender, disease duration before index date, smoking status, body mass index, COPD assessment score (e.g., CAT and mMRC), spirometry data (e.g., FEV₁), oxygen therapy, comorbidities, disease severity, previous exacerbation, previous treatments, or eosinophil counts, where appropriate.
 |
| Milestones: | 
Planned the start of data collection: July 2019
 
Planned the end of data collection: November 2019
 
Planned final study report: the end of January 2020
 |

Proprietary confidential information © 2019 Boehringer Ingelheim International GmbH or one or more of its affiliated companies

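### The between-cohort comparison of time to escalation sets LAMA-to-dual in cohort C against LABA/LAMA-to-triple in cohorts A and B, so a difference involving C cannot be read as a treatment effect on one event

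*Combined protocol and SAP*

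**What the plan says.** Section 9.1 assigns cohorts by the index-date prescription. Cohort A is on tiotropium/olodaterol, "cohort B is the patients treated with other LABA/LAMA therapy", and "cohort C is the patients receiving LAMA treatment". A and B therefore start on dual bronchodilation and C on a single agent.

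Section 9.3.2.2, like the variables entry of the abstract, defines the escalation outcome as the time and reason "from LABA/LAMA escalating to LABA/LAMA/ICS or from LAMA to dual therapy". A companion outcome has the same split: "Percentage of patients receiving LABA/LAMA switched to triple therapy or LAMA switched to dual therapy".

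The data analysis entry of the abstract treats escalation together with first exacerbation. Time to "escalating to dual or triple therapy will be compared between different cohorts using Kaplan-Meier curves", and "statistical significance will be assessed using log-rank tests". The same entry lists the study cohorts as "Tio + Olo vs. other LABA/LAMA vs. LAMA therapy".

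Section 9.7.1 says: "Time to escalating to dual/triple therapy will also be analysed using Kaplan-Meier curves and log-rank tests". It does not name the groups. The descriptive paragraph of section 9.7 mentions escalation to triple therapy only. Sections 4 and 9.7.1 apply a chi-square or Fisher test to categorical variables, with reasons for switching and percentages as examples.

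The study design entry of the abstract censors patients when they move from one LAMA/LABA or LAMA to another LAMA/LABA or to ICS.

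**The concern.** A log-rank test compares the hazard of one event between groups. Here cohort membership decides which event is counted. In C, when the step is to LABA/LAMA, the patient arrives at the regimen type on which A and B began. In A and B the event is the addition of ICS.

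The protocol itself suggests that these steps rest on different considerations. Section 9.3.3.2 ties ICS use to blood eosinophil counts and states nothing comparable for adding a second bronchodilator. The two steps may therefore occur at different rates whatever the index drug does. If LAMA-to-dual is the more frequent step, a significant result could be reported as tiotropium/olodaterol delaying escalation when it reflects only how the endpoint was defined.

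**Working it through.** **Check of the definition.** The plan gives no sample size, event count or rate for escalation, so there is no figure to reproduce. The relevant places, side by side:

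| Place | What counts as escalation | Groups compared |
|---|---|---|
| Section 4 (variables), 9.3.2.2 | LABA/LAMA to LABA/LAMA/ICS, or LAMA to dual | not stated |
| Section 4 (data analysis) | dual or triple | between cohorts; three listed in the entry |
| Section 9.7 | triple only | none (descriptive) |
| Section 9.7.1 | dual/triple | not stated |

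No visible passage limits the test to A versus B, separates the two steps, or argues that they can serve as one event. (The contents list shows a redacted entry between 9.7.1 and 9.7.3, which cannot be judged.)

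**Why matching does not help.** The candidate matching variables in section 9.7.1 are baseline characteristics. Two patients matched on all of them would still have different events counted if one is in A and the other in C.

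**Illustration of size.** Inputs:
- Cohort sizes: A about 300 and B about 800 (section 9.5). C = 1,800 − 300 − 800 = 700, by subtraction and not stated.
- Follow-up: 1 year (section 4).
- Two-sided 0.05, assumed; section 9.7.1 states 0.05 only for within-group changes.
- One-year step-up probabilities: assumed, 10% or 20% in A and B, 10% to 30% in C.

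With exponential times and no other censoring:

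- HR (C to A/B) = ln(1 − p_C) / ln(1 − p_AB)
- Events d = n_AB × p_AB + n_C × p_C
- P(reject) = Φ(|ln HR| × √(d × f × (1 − f)) − 1.96), where f is the A or B share of the two groups compared.

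Example, 10% against 15%, A versus C:
- HR = 0.1625 / 0.1054 = 1.54
- d = 300 × 0.10 + 700 × 0.15 = 135
- f = 300/1,000 = 0.30
- √(135 × 0.21) = 5.32
- P(reject) = Φ(0.433 × 5.32 − 1.96) = Φ(0.35) = 0.64

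| A/B | C | HR | A vs C: events, P(reject) | B vs C: events, P(reject) |
|---|---|---|---|---|
| 10% | 10% | 1.00 | 100, 0.05 | 150, 0.05 |
| 10% | 15% | 1.54 | 135, 0.64 | 185, 0.84 |
| 10% | 20% | 2.12 | 170, 0.99 | 220, >0.99 |
| 20% | 25% | 1.29 | 235, 0.43 | 335, 0.64 |
| 20% | 30% | 1.60 | 270, 0.94 | 370, 0.99 |

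A gap of five percentage points between the two kinds of step would often give significance at these sizes. Nothing in the test could say whether the gap came from the treatment or from the event definition.

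**Interaction with censoring.** Read literally, the abstract's rule censors a patient who moves to ICS, which is the escalation event in A and B. It can also be read as censoring a C patient who moves to LABA/LAMA. Section 9.7.1 repeats censoring at escalation to ICS only for the primary outcome, and no passage says how the rule applies when escalation is the endpoint.

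**The case against.** The best defence is that the mixed test is partly inferred. The abstract sentence covers two endpoints with one shared phrase about comparing cohorts. Section 9.7.1, the fuller text, uses that phrase only for the primary outcome, and an A-versus-B test would satisfy its line on escalation. This has some force, but section 9.7.1 neither restricts nor overrides the abstract, whose wording makes the comparison between cohorts.

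A second defence is that any step up from index therapy has one meaning everywhere: the index regimen was judged insufficient. Such an endpoint could be reported with caveats. The plan, however, neither defines nor justifies it, and it would not measure a treatment effect on one event.

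A reader might also infer more than the documents support:
- **That every escalation comparison with C is uninterpretable.** It can be described; what fails is the reading as a treatment effect on a single event.
- **That a known number of pairwise tests is invalid.** The plan sets out no pairwise log-rank tests.
- **That the percentage switched will be chi-square tested across all three cohorts.** The wording allows this but does not say it.
- **That A versus B is fully like with like.** Both admit patients switched from single, dual or triple therapy. For someone who came from triple therapy the event is a return to ICS, and that share may differ between A and B.
- **That C's event is always the addition of one agent.** Dual therapy is not defined in the outcome, and the medication list includes LABA + ICS.

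**Conclusion.** The concern holds. As the abstract is written, a log-rank comparison of escalation involving cohort C sets different events against each other, and a difference could arise from the definitions alone. The same applies to the percentage switched if it is tested across all three cohorts. A versus B shares one event definition and is not affected by this problem.

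C makes up about 700 of 1,800 patients (39%), on the assumption that it is the remainder after A and B. The rejection probabilities in the table rest wholly on assumed step-up rates. They show that the mismatch could produce significance, not that it will, and the true direction is unknown. This is a secondary outcome in a retrospective chart review, so the primary comparison of exacerbations is not touched. It is still more than a missing detail, because following the text could yield a significant but misleading result.

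**What to change.** 1. Limit the formal log-rank test of time to escalation, and any chi-square test of the percentage switched, to A versus B, with the step to LABA/LAMA/ICS as the event. Note that A and B may differ in the share switched from prior triple therapy; previous treatment is already a candidate matching variable.
2. Report C's LAMA-to-dual time and percentage descriptively, and say which regimens count as dual therapy.
3. If a three-cohort comparison is kept, use one event with the same meaning in all cohorts, for example first ICS-containing regimen or first triple therapy. State its limits: the cohorts start at different distances from triple therapy, and A and B may include earlier ICS users.
4. Align the abstract's data analysis entry with sections 9.7 and 9.7.1 on both the event and the groups.
5. Reconcile the analysis censoring rule in the abstract's study design entry with this endpoint, so that it does not censor the escalation event itself.

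The cost is protocol wording. Prescription dates and reasons for switching are already collected (Table 1 notes and section 9.3.3.7), so no new data are needed. The downside is that under steps 1 and 2 the formal escalation tests involving cohort C are lost.
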